03 NOV 2020

Version 11.0

Page: 49 of 259

Table 9–1: Schedule of procedures and assessments in part 1 – Study 16027

Phase	Screening	Treatment Phase				Fol	Follow-up Phase				
Visit	1	2	3	4 ^a	5 ^a	6	7 ^a	8 (EOT) ^b	9	10	11
Day	-14 to -1	1 °	7 ± 1	14 ± 1	21 ± 3	30 ± 3	42 ± 3	60 ± 3	90 ± 7	240 ± 7	420 ± 7

^p At Visit 6 (Day 30), subjects will return all remaining study drug and empty packaging, and study drug for the remaining 30 days of treatment will be dispensed.

^q A pre-paid phone card will be provided at Visits 3 and 6 to facilitate contact between study site personnel and the subjects/subjects' authorized representatives at Visits 4, 5, and 7.

* IHA will be performed at Visit 1 and Visit 11 only, if adequate specimens are available

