## 6.2.1.3 Exploratory efficacy analysis and analysis

For the exploratory objective to assess the comparability of nifurtimox with benznidazole, the cure rate of 58% with a 95% CI (45%, 70%) from publication of de Andrade et al. in 1996 [2] will be referenced. If the lower limit of the same 95% CI for the primary efficacy variable (the 60-day nifurtimox regimen cure rate) is greater than 45%, nifurtimox will be deemed as comparable to benznidazole.

The comparison of conventional serology to IHA results will be done using a 3-by-3 table (Table 6-2) with the following categories:

- ELISA tests: sero-conversion and sero-positive (sub-categories: sero-reduction and others), where "others" refers to any sero-positive results that do not satisfy the definition of "sero-reduction".
- IHA test: negative and positive (sub-categories: titers decreasing and titers non-decreasing).

BAY No. A2502/IMPACT No. 16027

21 of 30

Page:

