#### Table 6–2 Summary table of comparison between serology and IHA results

						Conventi	ional ELISA Tes	ts
				Sero-	Sero-pos	itive	Missing	Total
				negative	Sero-reduction	Others		
	60-Day	Negative		xx (xx.x%)	xx (xx.x%)	xx (xx.x%)	xx (xx.x%)	xx (xx.x%)
	(N=x)		Decreasing in	xx (xx.x%)	xx (xx.x%)	xx (xx.x%)	xx (xx.x%)	xx (xx.x%)
		Positive	titers					
		TOSITIVE	Non-decreasing	xx (xx.x%)	xx (xx.x%)	xx (xx.x%)	xx (xx.x%)	xx (xx.x%)
			in titers					
		Missing		xx (xx.x%)	xx (xx.x%)	xx (xx.x%)	xx (xx.x%)	xx (xx.x%)
		Total		xx (xx.x%)	xx (xx.x%)	xx (xx.x%)	xx (xx.x%)	xx (xx.x%)
ША								
Tasting	30-Day	Negative		xx (xx.x%)	xx (xx.x%)	xx (xx.x%)	xx (xx.x%)	xx (xx.x%)
resting	(N=x)		Decreasing in	xx (xx.x%)	xx (xx.x%)	xx (xx.x%)	xx (xx.x%)	xx (xx.x%)
		Positivo	titers					
		rositive	Non-decreasing	xx (xx.x%)	xx (xx.x%)	xx (xx.x%)	xx (xx.x%)	xx (xx.x%)
			in titers					
		Missing		xx (xx.x%)	xx (xx.x%)	xx (xx.x%)	xx (xx.x%)	xx (xx.x%)
		Total		xx (xx.x%)	xx (xx.x%)	xx (xx.x%)	xx (xx.x%)	xx (xx.x%)

In addition, McNemar's test will be performed by treatment regimen for all patients in FAS (Table 6–3) with the following categories:

- ELISA tests: cure (sero-conversion and sero-reduction) versus no cure;
- IHA test: negative or positive but decreasing in titers versus positive but non-decreasing in titers.

Table 6–3 McNemar's test on comparison between serology and IHA results for all patients in FAS

				Cor	nventional ELISA	Tests		
			Cure (sero- negative or sero- reduction)	No cure	Missing	Total	$\chi^2$	P-Value
	60-Day (N=x)	Negative or positive but decreasing in titers	xx (xx.x%)	xx (xx.x%)	xx (xx.x%)	xx (xx.x%)		
		Positive but non- decreasing in titers	xx (xx.x%)	xx (xx.x%)	xx (xx.x%)	xx (xx.x%)		
		Missing	xx (xx.x%)	xx (xx.x%)	xx (xx.x%)	xx (xx.x%)		
		Total	xx (xx.x%)	xx (xx.x%)	xx (xx.x%)	xx (xx.x%)	X.XX	X.XX
IHA Testing	30-Day (N=x)	Negative or positive but decreasing in titers	xx (xx.x%)	xx (xx.x%)	xx (xx.x%)	xx (xx.x%)		
		Positive but non- decreasing in titers	xx (xx.x%)	xx (xx.x%)	xx (xx.x%)	xx (xx.x%)		
		Missing Total	xx (xx.x%) xx (xx.x%)	xx (xx.x%) xx (xx.x%)	xx (xx.x%) xx (xx.x%)	xx (xx.x%) xx (xx.x%)	x.xx	X.XX

The same test would also be performed by treatment regimen in sero-positive subjects (Table 6–4). The categories for this test are

- ELISA tests: sero-reduction versus others (sero-positive that are not sero-reduction);
- IHA test: negative or positive but decreasing in titers versus positive but non-decreasing in titers.

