## Table 6–4 McNemar's test on comparison between serology and IHA results for all sero-positive patients in FAS

				Cor	ventional ELISA	Tests		
			Sero-reduction	Others	Missing	Total	$\chi^2$	P-Value
	60-Day (N=x)	Negative or positive but decreasing in titers	xx (xx.x%)	xx (xx.x%)	xx (xx.x%)	xx (xx.x%)		
		Positive but non- decreasing in titers	xx (xx.x%)	xx (xx.x%)	xx (xx.x%)	xx (xx.x%)		
		Missing	xx (xx.x%)	xx (xx.x%)	xx (xx.x%)	xx (xx.x%)		
		Total	xx (xx.x%)	xx (xx.x%)	xx (xx.x%)	xx (xx.x%)	X.XX	X.XX
IHA Testing	30-Day (N=x)	Negative or positive but decreasing in titers	xx (xx.x%)	xx (xx.x%)	xx (xx.x%)	xx (xx.x%)		
		Positive but non- decreasing in titers	xx (xx.x%)	xx (xx.x%)	xx (xx.x%)	xx (xx.x%)		
		Missing Total	xx (xx.x%) xx (xx.x%)	xx (xx.x%) xx (xx.x%)	xx (xx.x%) xx (xx.x%)	xx (xx.x%) xx (xx.x%)	x.xx	X.XX

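### Table 6-4 selects children on ELISA but not on IHA, so any shift the selection causes favours IHA and the McNemar p-value cannot be read as disagreement between the assays (minor, exploratory)

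*SAP*

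**What the plan says.** SAP 6.2.1.3 first sorts the ELISA result: "ELISA tests: sero-conversion and sero-positive (sub-categories: sero-reduction and others), where" the residual group "refers to any sero-positive results that do not satisfy the definition of" sero-reduction. Sero-positive is thus the alternative to having converted.

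Two McNemar tests follow, each by regimen.

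- **Table 6-3, whole FAS.** "ELISA tests: cure (sero-conversion and sero-reduction) versus no cure", against "IHA test: negative or positive but decreasing in titers versus positive but non-decreasing in titers".
- **Table 6-4.** "The same test would also be performed by treatment regimen in sero-positive subjects"; the table title reads "comparison between serology and IHA results for all sero-positive patients in FAS". The ELISA split becomes "ELISA tests: sero-reduction versus others (sero-positive that are not sero-reduction"). The IHA split is carried over unchanged, so an IHA-negative child is still an IHA responder.

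The SAP does not print the time point beside Table 6-4, but it must be Visit 11. The footnote to protocol Table 9-1 states "IHA will be performed at Visit 1 and Visit 11 only, if adequate specimens are available", and sero-reduction exists only after baseline. A baseline reading of sero-positive would also leave converters with no column in Table 6-4.

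The SAP gives no reason for the one-sided restriction and no rule for interpreting the result.

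**The concern.** McNemar's test uses only the discordant pairs and asks whether the two kinds are equally frequent. Choosing the analysis set by the result of one member of the pair can unbalance those counts without any difference between the assays. Here the best ELISA outcome is removed and the best IHA outcome is kept.

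Comparing conventional serology with IHA is a stated exploratory objective (protocol 4.1, SAP 2.1). IHA was brought in because the regulator asked for a second serological test to validate the ELISA results (protocol 15.6.1). Table 6-4 is the only planned test that looks at ELISA sero-reduction apart from conversion. A small p-value favouring IHA could be reported as the assays disagreeing about children who have not converted, when the selection alone may have produced it.

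**Working it through.** The plan gives no sample size, discordance rate or expected result for these tests, and Tables 6-2 to 6-4 are empty shells. There is no planned figure to reproduce.

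**1. Counts.** Give each assay three states: N (negative), R (positive and responding: ELISA sero-reduction, or IHA titer falling) and P (positive, not responding). Let x(i,j) be the number of children with ELISA state i and IHA state j. McNemar's statistic is (b − c)² / (b + c), where b counts ELISA-only responders and c counts IHA-only responders.

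- Table 6-3: b = x(N,P) + x(R,P); c = x(P,N) + x(P,R).
- Table 6-4 (rows R and P only): b′ = x(R,P) = b − k, with k = x(N,P); c′ = c.
- Positive on both assays: b″ = x(R,P); c″ = x(P,R).

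The restriction takes k pairs from b and none from c. If b = c in the full set, the difference can move only towards IHA. If k = 0, nothing changes.

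**2. Symmetric example (assumed cells).** N = 200, 55% response and 20% negative on each assay, so each assay has 40 in N, 70 in R and 90 in P. Take x(N,P) = x(P,N) = 10 and x(R,P) = x(P,R) = 10.

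- Full set: b = 20, c = 20, statistic 0, p = 1.0.
- Table 6-4 set, n = 200 − 40 = 160: b′ = 10, c′ = 20, statistic (10 − 20)² / 30 = 3.33, p = 0.068. ELISA response is 70/160 = 43.8% and IHA response is (70 − 10 + 20)/160 = 50.0%, although the two assays are identical by construction.
- Positive on both: b″ = 10, c″ = 10, p = 1.0.

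**3. Simulation.** From the documents: two-sided 5% level (SAP 4.1); about 300 children randomized 2:1, so about 200 and 100 per regimen (SAP 3.1, protocol 10.4); 55% response (SAP 6.5), applied here to both assays. Assumed: exchangeable assays with bivariate normal readings and identical cut-offs, the share converted, and the correlation. The test is asymptotic McNemar without continuity correction, with 20,000 runs per setting. Rejection rate of the Table 6-4 test, n = 200 / n = 100:

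| Converted | r = 0.4 | r = 0.5 | r = 0.7 | r = 0.9 |
|---|---|---|---|---|
| 10% | 7% / 6% | 6% / 6% | 5% / 5% | 6% / 5% |
| 20% | 21% / 13% | 15% / 10% | 7% / 7% | 5% / 5% |
| 25% | 36% / 21% | 26% / 16% | 11% / 8% | 5% / 5% |

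Where the rate is clearly raised, nearly all rejections favour IHA: at n = 200, 20% converted and r = 0.5, 14.9 of the 15.2 percentage points. Mean discordant counts there go from 33 against 33 to 26 against 33. The unrestricted and both-positive tests stay between 4.5% and 5.7% throughout. At a correlation as low as 0.3, even 10% converted gives about 10% (n = 200).

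**4. A related asymmetry, not counted above.** Sero-reduction is defined only for children aged at least 8 months at randomization (SAP 6.2.1.1). If that limit also applies in Table 6-4, a younger infant who stays ELISA-positive can fall only under others, and so can add to c but never to b.

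**The case against.** **The test is valid for its own question.** In a subset, McNemar tests whether the two response proportions are equal within that subset, and it holds about its nominal level for that hypothesis. This stands. A reader might infer that the Table 6-4 null is false by construction. The documents do not support that: nothing shifts when k = 0, and the rates above are rejections under exchangeable assays, a hypothesis the SAP never states. The fault is in what the p-value can be taken to mean.

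**The size is uncertain and may be nil.** A reader might also infer a large inflation by arguing that infants make 20 to 25% conversion likely. Two strata under 8 months at 38 each are 76 of 300, about 25%, and protocol 5.1 cites negative conventional serology at 6.6 months in treated infants. But the 38 is targeted and not required. Infants who convert on both assays are also not in the cell that causes the shift. With 25% infants converting at 75% on each assay and older children at 2 to 5%, the rejection rate was 4.9 to 6.5%; raising older-child conversion to 10% gave 9 to 13% at correlations of 0.3 to 0.5. Setting infant response at 80%, with older-child conversion at 2 to 5%, gave 8 to 17%. All of these inputs are assumed. What stands is that the documents fix the direction but not the size.

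**The information is already displayed.** Table 6-2 prints every cell, including those dropped, and Table 6-3 runs the unselected test. This limits the harm, but it does not make the Table 6-4 p-value interpretable.

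**The remedy has its own loss.** ELISA-positive, IHA-negative children are informative when IHA serves to check ELISA, and a both-positive set would omit them from the test. This is fair; they remain visible in Table 6-2.

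**Conclusion.** The concern holds as a minor point. Table 6-4 conditions on one of two paired results, the resulting shift can run only towards IHA, and its p-value should not be reported as evidence that the assays disagree. That conclusion follows from the table definitions alone.

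The size rests on assumptions. It runs from nothing, through about 5 to 7% when about 10% have converted and the correlation is 0.4 or more, to 7 to 11% (correlation 0.7) or 15 to 26% (correlation 0.5) with 20 to 25% converted and n = 200. In the 30-day arm the corresponding figures are about 7 to 8% and 10 to 16%. IHA depends on adequate specimens, so actual numbers may be smaller.

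The analysis is exploratory and no decision rule is attached to it. The primary endpoint does not use IHA, and Table 6-3 is free of this selection.

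**What to change.** Either of two changes to SAP 6.2.1.3 is enough.

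1. Define the Table 6-4 set as FAS children positive on both ELISA and IHA at Visit 11. Compare ELISA sero-reduction against others with IHA titer decreasing against not decreasing, and remove the IHA-negative category from this table. This gives an exact null only if the assays are exchangeable, and the SAP should say so.
2. Drop the Table 6-4 p-value and describe the ELISA-positive columns of Table 6-2.

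Under either, report how many children are ELISA-negative only, IHA-negative only and negative on both, and state how infants under 8 months are classified. The ELISA Missing column can be removed from Table 6-4 in the same edit, since it does not fit a set defined as ELISA-positive.

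The cost is one subset condition and a sentence or two of SAP text, with no new data. The first option leaves slightly fewer children in an exploratory test, and ELISA-positive, IHA-negative children would then appear only in Table 6-2.

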## Table 6–4 McNemar's test on comparison between serology and IHA results for all sero-positive patients in FAS

				Cor	ventional ELISA	Tests		
			Sero-reduction	Others	Missing	Total	$\chi^2$	P-Value
	60-Day (N=x)	Negative or positive but decreasing in titers	xx (xx.x%)	xx (xx.x%)	xx (xx.x%)	xx (xx.x%)		
		Positive but non- decreasing in titers	xx (xx.x%)	xx (xx.x%)	xx (xx.x%)	xx (xx.x%)		
		Missing	xx (xx.x%)	xx (xx.x%)	xx (xx.x%)	xx (xx.x%)		
		Total	xx (xx.x%)	xx (xx.x%)	xx (xx.x%)	xx (xx.x%)	X.XX	X.XX
IHA Testing	30-Day (N=x)	Negative or positive but decreasing in titers	xx (xx.x%)	xx (xx.x%)	xx (xx.x%)	xx (xx.x%)		
		Positive but non- decreasing in titers	xx (xx.x%)	xx (xx.x%)	xx (xx.x%)	xx (xx.x%)		
		Missing Total	xx (xx.x%) xx (xx.x%)	xx (xx.x%) xx (xx.x%)	xx (xx.x%) xx (xx.x%)	xx (xx.x%) xx (xx.x%)	x.xx	X.XX

## 6.2.2 Part 2 (CHICO SECURE)

## 6.2.2.1 Primary efficacy variable and analysis

## Primary efficacy variable

The primary efficacy variable will be the incidence rate of seronegative conversion measured and confirmed by two types of assay (recombinant ELISA and IHA) in subjects who were randomized and received at least one dose of the 60-day nifurtimox treatment regimen. Both test results should be negative for the subject to be considered as seroconverted. Incidence rate is the number of new cases of seronegative conversion over the study period (i.e. 4 years after end of nifurtimox treatment) divided by the person-time at risk.

Subjects used antitrypanosomal drugs during the study before they were seroconverted will not be considered as sero-convertion, but their time of observation till when they took antitrypanosomal drugs will be factored into the person time calculation.

#### Primary analysis of the primary efficacy variable

The difference in the incidence rate of nifurtimox subjects with seronegative conversion (60-day regimen) and the seronegative rate estimated from historical data will be tested using a Poisson two-sided 95% exact confidence interval (CI).

## BAY No. A2502/IMPACT No. 16027 Page: 23 of 30

The incidence rate of seronegative conversion for the primary efficacy variable will be modelled using a Poisson distribution with a 2-sided 95% exact CI. The rate will be estimated as the number of seronegative conversion divided by the total time at risk (person-year) during the study. The rate of seronegative conversion (R) and a 2-sided limits ( $R_l$ ,  $R_u$ ) of the 95% CI for the rate can be calculated using the following formula [4]

$$R = \frac{n}{\sum_{i} N_i * V_i}, i = 1, 2, ... K$$

$$R_{l} = \frac{\chi^{2}_{2n,\alpha/2}}{2\sum_{t} N_{t} * V_{t}}, i = 1, 2, ... K$$

$$R_{u} = \frac{\chi^{2}_{2(n+1),1-\alpha/2}}{2\sum_{i} N_{i} * V_{i}}, i = 1, 2, \dots K$$

where n is the number of seronegative conversion observed, N the total subjects at risk in annual visit *i*, Vi the *i*th annual visit, *K* the total number of visits,  $R_i$  and  $R_u$  are lower and upper confidence limits for the rate of seronegative conversion respectively,  $\chi^2_{\nu,a}$  is the chi-square quantile for upper tail probability on v degrees of freedom.

This study uses an external control group of untreated patients with Chagas' disease in the 4-year follow-up period presented in Sosa et al. [7, 7]. In the reference, seroconversion to a negative result in the placebo group after 4-year follow-up was detected in 2 subjects with conventional serology and in 0 subjects with IHA test. Thus, none of the subjects in the placebo group was considered as seroconverted by both test results. The person time at risk was on average 44 \* 4 = 176 person years. The incidence rate estimate was 0% (0 / 176).

Superiority will be confirmed if the lower limit of the CI for the incidence rate of seronegative conversion for subjects in 60-day regimen is greater than the rate of historical placebo subjects with sero-conversion (i.e. 0 %).

Frequency counts and percentages of seronegative conversion will be provided by visit.

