03 NOV 2020

Plan for statistical analysis	Part 1 (CHICO)
	Primary efficacy analysis
	The difference in the proportion of nifurtimox subjects with sero-reduction or sero-conversion (60-day regimen) and the proportion estimated from historical data will be tested using a 2-sided 95% confidence interval (CI) for a single proportion. ²⁵
	Superiority will be confirmed if the lower limit of the CI for the proportion of nifurtimox subjects (60-day regimen) with seroreduction or sero-conversion is greater than the proportion of historical placebo subjects with sero-conversion. ²⁶
	Secondary efficacy analysis
	A secondary analysis will be done to compare the proportion of subjects with sero-reduction or sero-conversion for the 60-day and 30-day nifurtimox regimens. This will be performed using a 2-sided 95% CI for the difference of two independent proportions. ²⁷
	The analyses specified above will also be done using data from the EOT visit, and 3 and 6 months after EOT.
	The relationship of conventional serology results to qPCR results will be done using frequencies of matches and mismatches on the determination of disease status, and phi-correlation and kappa coefficient to assess the degree of agreement. The relationship of non-conventional serology to conventional serology will be analyzed in the same way. ²⁸
	The primary efficacy analysis will be done using the full analysis set, which is the set of subjects who received at least one dose of study drug. Analyses will also be done using the per-protocol set, which is comprised of subjects treated with study drug who have no major protocol deviations.
	According to Guhl et al. (2004), nifurtimox 12 months post- treatment cure rate is about 55%, with a sample size of 200 for the 60-day regimen, the power is 99% for the lower limit of the 95% CI to be greater than 16%, a performance goal based on historical study. ²⁹
	gour oused on instorteur study.
	Part 2 (CHICO SECURE)
	Primary efficacy analysis
	The difference in the incidence rate of nifurtimox subjects with seronegative conversion (60-day regimen) and the rate estimated from historical data will be tested using a Poisson two-sided 95% confidence interval (CI).
	The incidence rate of seronegative conversion for the primary efficacy variable will be modelled using a Poisson distribution with a 2-sided 95% CI. The rate will be estimated as the number of seronegative conversion divided by the time at risk of event (person-year) during the study.

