There are several choices for diagnosis of Chagas' disease and monitoring of drug efficacy after anti-parasitic treatment. Traditional parasitological methods, such as direct microscopic observation, xenodiagnoses, and hemoculture, show low sensitivities, limiting their usefulness. Microhematocrit is the method of choice to identify congenital infection because of its heightened sensitivity and the small amount of blood needed. Microscopic examination of cord blood or peripheral blood of the neonate by this technique is strongly recommended during the first month of life. For the monitoring of drug efficacy, the criterion of cure usually depends on serologic conversion of the anti-*T. cruzi* antibody response to negative. Sero-conversion in children and adolescents may occur several years after treatment, requiring long-term follow-up.

Sero-reduction (measured as a $\geq 20\%$ reduction of the ELISA absorbance [OD] value) at 12 months post-treatment will be considered equivalent to historical information on sero-conversion at subsequent time points after treatment.⁷²

Both primary and secondary study endpoints are based upon a target of $\geq 20\%$ decrease in antibody concentration (sero-reduction) to *T. cruzi* in conventional serological tests or negativization of serology. This is consistent with one previous study in children 6 to 12 years of age infected with *T. cruzi* in the intermediate (early chronic) phase of Chagas' disease [15]. Subjects were administered 5mg/kg benznidazole or placebo in a randomized fashion for 60 days, and followed for 48 months. At 12 months, a 21% reduction in concentration of Chagas' disease-specific antibodies compared to baseline (ELISA mean OD 0.467 [± 0.099] vs. 0.369 [± 0.107]) was observed in subjects who received benznidazole. For the subsequent time points of 18, 24, and 48 months, percent concentration reductions in antibody titer were reported as 23%, 29%, and 27%, respectively. After a 48-month follow-up, negative sero-conversion was detected in 11.3% (P<0.05) of the benznidazole group and only 4.5% of the placebo group.⁷³

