10.3.2.2 Part 2 (CHICO SECURE)

Analysis of the primary efficacy variable

The difference in the incidence rate of nifurtimox subjects with seronegative conversion (60-day regimen) and the rate estimated from historical data will be tested using a Poisson two-sided 95% exact confidence interval (CI).

The incidence rate of seronegative conversion for the primary efficacy variable will be modelled using a Poisson distribution with a 2-sided 95% exact CI. The rate will be estimated as the number of seronegative conversion divided by the time at risk of event (person-year) during the study. The rate of seronegative conversion () and a 2-sided limits (,) of the 95% CI for the rate can be calculated using the following formula [34]:

¹⁹¹ Modified as per amendment 2

¹⁹² Text modified/added for clarity as per Modification 2 (Amendment 1)

¹⁹³ Modified as per amendment 4

	Integrated Clinical Study Protocol BAY A2502/ 16027		
03 NOV 2020	Version 11.0	Page:	82 of 259

where n is the number of seronegative conversion observed , N the total subjects at risk in annual visit , V_i the th annual visit, the total number of visits, and are lower and upper confidence limits for the rate of seronegative conversion respectively, is the chi-square quantile for upper tail probability on v degrees of freedom.

This study uses an external control group of untreated patients with Chagas' disease in the 4year follow-up period presented in Sosa et al. [15, 35]. In the reference, seroconversion to a negative result in the placebo group after 4-year follow-up was detected in 2 subjects with conventional serology and in 0 subjects with IHA test. Thus, none of the subjects in the placebo group was considered as seroconverted by both test results. The person time at risk was on average 44 * 4 = 176 person years. The incidence rate estimate was 0% (0 / 176).

Superiority will be confirmed if the lower limit of the CI for the incidence rate of seronegative conversion for subjects in 60-day regimen is greater than the rate of historical placebo subjects with sero-conversion (i.e. 0 %).

No imputations will be made for missing data due to dropouts or other causes, as person-year is considered in the calculation of incidence rate.

Frequency counts and percentages of seronegative conversion will be provided by visit.

Missing data/drop outs

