#### Table 6–1: Historical Cure Rates for Placebo

Publication	Age range (in years)	Sero-conversion rate (95%Cl) in placebo patients
de Andrade et al 1996	7-12	3/65 = 5% (1%,13%)
Sosa et al 1998	6 -12	2/44= 5% (1%,16%)

Both publications show a 5% cure rate for the placebo group. For the primary objective in our study, superiority over placebo will be confirmed if the lower limit of the 95% CI for the nifurtimox (60-day regimen) cure rate is greater than 16%, the larger of the upper limits of the 95% CIs from the two publications.

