## Part 2 (CHICO SECURE)

According to Sosa-Estani [7, 7], the 48 months post treatment cure rate for benznidazole is about 5% as confirmed by two types of assay. For the primary objective, assuming a drop-out rate of 15%, the expected number of patients to be observed at the end of Part 2 (i.e. 48 months post treatment) in the 60-day regimen would be 170 out of the 200 patients in Part 1. Using the assumptions of 170 nifurtimox 60-day regimen patients in Part 2, a 5% cure rate, and that seronegative conversion events follow Poisson distribution, the estimated incidence rate is calculated to be 1.32% and the 95% CI of the incidence rate is (0.61%, 1.51%).

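### The Part 2 superiority rule compares the 60-day lower limit with a control rate fixed at 0%, so under the exact Poisson interval a single conversion passes and the control's uncertainty is ignored

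*SAP*

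**What the plan says.** The Part 2 primary variable is the rate of conversion to negative on both recombinant ELISA and IHA in the 60-day arm. SAP 6.2.2.1 and protocol 10.3.2.2 both specify a two-sided 95% exact Poisson interval for that arm alone.

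- **Rule.** In the SAP, superiority holds if the lower limit "for subjects in 60-day regimen is greater than the rate of historical placebo subjects with sero-conversion (i.e. 0" per cent. Protocol 10.3.2.2 says the same: the lower limit "is greater than the rate of historical placebo subjects with sero-conversion (i.e. 0" per cent.
- **Synopsis.** The Part 2 analysis paragraph says the difference "will be tested using a Poisson two-sided 95% confidence interval (CI"), without the word 'exact', and then gives the same superiority rule and the same control figures.
- **Control.** In the cited trial's placebo group (44 children, 4 years), conversion "was detected in 2 subjects with conventional serology and in 0 subjects with IHA test", so none converted on both. The SAP concludes: "The incidence rate estimate was 0% (0 / 176"). No interval is given for that rate.
- **Part 1, for contrast.** The text under SAP Table 6–1 sets the bar at 16%, described as "the larger of the upper limits of the 95% CIs from the two publications", and not at the 5% point estimate.
- **Planning.** SAP 6.5: "Using the assumptions of 170 nifurtimox 60-day regimen patients in Part 2, a 5% cure rate", the plan obtains a rate of 1.32%. It gives no power for the Part 2 rule.

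**The concern.** An exact Poisson lower limit is zero only when there are no events. Setting the bar at 0% therefore turns the superiority test into a check that at least one child converted. The cause is that 0 events in 176 PY is called an estimate and then used as a known constant.

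At stake is the primary Part 2 conclusion. The rate, its interval and the counts by visit would remain informative, but the words 'superiority confirmed' could be attached to data that do not separate the treated arm from the control. Part 2 takes its control from one of the two Part 1 publications yet drops the allowance made in Part 1, and no reason is given.

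**Working it through.** **Inputs.** Control: 0 events, 44 × 4 = 176 PY (SAP 6.2.2.1). Planned 60-day arm: 170 children, 5% converting over 4 years (SAP 6.5), hence 170 × 4 = 680 PY and 170 × 0.05 = 8.5 events, rounded to 9. Final person-time is not fixed in advance: SAP 4.3 counts drop-outs' time, and SAP 6.2.2.1 stops time at antitrypanosomal treatment. I therefore also use 600 and 740 PY as an assumed range.

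**1. The plan's own figure.** Rate = 9/680 = 1.32 per 100 PY. Lower limit = χ²(0.025; 18)/(2 × 680) = 0.61. Both match SAP 6.5. The upper limit is χ²(0.975; 20)/(2 × 680) = 2.51, where the plan prints 1.51. The superiority rule does not use the upper limit.

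**2. One conversion.** Lower limit = χ²(0.025; 2)/(2T) = 0.0253/T, above 0 for every finite T. Per 100 PY it is 0.0042, 0.0037 and 0.0034 at 600, 680 and 740 PY. With no conversions it is 0 and the rule fails. The SAP labels its chi-square quantile as upper-tail; read literally, one event gives 3.69/T (0.54 per 100 PY at 680), which also passes. At the planned mean of 8.5 events the rule passes with probability 1 − exp(−8.5) = 99.98%.

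The synopsis does not say 'exact', so the one-event result is not claimed there. A normal-approximation interval, n ± 1.96√n, would first clear zero at n = 4 (4 − 3.92 = 0.08).

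**3. What 0 in 176 PY shows.** Exact upper limit = χ²(0.975; 2)/(2 × 176) = 2.10 per 100 PY, above the planned treated rate of 1.32. True rates of 0.1, 0.5 or 1.0 per 100 PY would give no events in 176 PY with probability exp(−176 × rate) = 84%, 41% or 17%.

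**4. False passes (illustration only).** For a drug with no effect, P(pass) = 1 − exp(−T × rate):

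| Assumed untreated rate per 100 PY | 600 PY | 680 PY | 740 PY |
|---|---|---|---|
| 0.01 | 6% | 7% | 7% |
| 0.1 | 45% | 49% | 52% |
| 0.5 | 95% | 97% | 98% |

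At 680 PY the false-pass rate is at most 2.5% only if the untreated rate is at most −ln(0.975)/680 = 0.0037 per 100 PY.

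**5. The planning result, tested with the control's uncertainty.** With no control events, the exact conditional one-sided p is [T/(T + 176)]ⁿ. For n = 9 and T = 680 this is (680/856)⁹ = 0.126 (0.099 at 600 PY, 0.147 at 740 PY).

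**6. Conversions needed under a repaired rule.**

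| Rule | 600 PY | 680 PY | 740 PY |
|---|---|---|---|
| Conditional test, one-sided p < 0.025 | 15 | 17 | 18 |
| Lower limit above 2.10 per 100 PY | 21 | 23 | 25 |

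Power at 680 PY (Poisson): 0.7% and 0.003% at a mean of 8.5 events; 96% and 68% at an assumed 25; over 99% and about 99% at an assumed 35.

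**The case against.** **The untreated two-assay rate may be practically zero.** Against a bar of exactly 0 the rule makes no type I error, and the only two-assay untreated observation is 0/176. Protocol 5.1 also reports that placebo antibody levels in the other historical trial fell at first and then rose. This stands as a possibility. But the same trial's placebo group had 3/65 conversions on its own measure (SAP Table 6–1), and 0/176 does not establish zero.

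**The actual count may be far above nine.** This also stands. The control trial is described as "one previous study in children 6 to 12 years of age", while protocol 6.1 enrols from birth. Protocol 5.1 cites 21 congenital cases treated with benznidazole: those diagnosed before 8 months of age became negative on conventional serology at 6.6 months, the older group at 63.1 months. That is not the two-assay endpoint, but with 25 to 35 conversions the present and repaired rules would usually agree.

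**Nothing is hidden.** The rate, exact CI and counts by visit are pre-specified. True, but that does not make the decision rule sound.

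**Stronger readings.** A reader might infer that the false-positive rate is 49% or 97%; those figures rest on untreated rates the documents do not give. A reader might take the 2 single-assay conversions in 176 PY (1.14 per 100 PY) as a ceiling on the untreated rate. It is a point estimate for one assay, with exact 95% CI 0.14 to 4.10, and bounds nothing. A reader might also conclude that the formal Part 2 test must go. A repaired rule is enough, and Part 2 was designed at FDA's request, although the documents do not say whether FDA agreed this rule.

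**Conclusion.** The rule is wrong as written. In SAP 6.2.2.1 and protocol 10.3.2.2 it amounts to requiring one conversion. That consequence needs no assumption about person-time and holds on either reading of the chi-square quantile. The synopsis carries the same 0% bar, with an interval not called exact.

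The size of the problem is best seen in the planning case, which would pass at one-sided p = 0.126, assuming 680 PY and 9 events. How often the rule would mislead in practice depends on the untreated two-assay rate and on the number of conversions, and the documents settle neither. The defect lies in the decision rule, not in the estimated rate. It does not show that nifurtimox lacks an effect or that Part 2 could not demonstrate one.

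**What to change.** In SAP 6.2.2.1, protocol 10.3.2.2 and the synopsis:

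- Keep the 60-day rate with its exact 95% CI, and call the synopsis interval exact.
- Report the control as 0 events in 176 PY with exact 95% CI 0 to 2.1 per 100 PY, and state that the groups are not age-matched.
- Replace the superiority sentence with:

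> Superiority will be concluded only if an exact conditional test of equal Poisson rates (60-day arm versus 0 events in 176 person-years), at the observed person-time, gives one-sided p < 0.025; otherwise the comparison is descriptive.

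A rule in the Part 1 style, with the 60-day lower limit above the control's upper limit, is an acceptable alternative. Either should be written as a method applied at the observed person-time, not as a fixed count.

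**Cost.** No new data: revised wording in three places and one short calculation. The near-automatic superiority label is lost, and at the planned 8.5 events power falls below 1% under either rule. The test covers sampling error only. It does not adjust for differences between this trial's population and the historical control.
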